7.1.2.4. Dose Expansion Weekly Dosing Schedule for Lymphomas

Time and Events Table for Full Study (Cycle = 28 days)									
Study Assessments ¹	Screen ²	Day 1 C1	Day 8 C1	Day 15 C1	Day 1 C2	Day 15 C2	D1 of C3-C16	End of Study Treatment	3-Month Off-study Follow-up
Informed Consent	X								
Baseline Demographics	X								
Medical History	X								
Physical Exam	X	X			X		At the start of each cycle	X	
Ocular Exam	X ³				X ⁴		At the start of each cycle ⁴	X ⁴	
ECOG Performance Status	X				X		At the start of each cycle	X	
Vital Signs (BP, HR, Body Temperature)	X	X ⁵	X ⁵	X ⁵	X ⁵		At the start of each cycle ⁵	X	
Weight and Height	X	Weight only			Weight only		Weight only - At the start of each cycle	Weight	
Hematology	X	X ⁶	X	X	X		At the start of each cycle	X	
Clinical chemistry	X	X ⁶	X	X	X	X	At the start of each cycle	X	
Urine Dipstick	X	X ⁶			X		At the start of each cycle	X	
INR, PTT	X	X ⁶	X	X	X		At the start of each cycle		
HBV/HCV tests	X								
CK-MB , Troponin	X ⁷		X ⁷		X ⁷		At the start of each cycle ⁷	X ⁷	
BNP	X ⁸								
24 hr urine protein and albumin	X				X		At the start of each cycle		
IgG, IgM, IgA	X				X		At the start of every other cycle		
CRP, beta2 microglobulin	X				X		At the start of each cycle		
Pregnancy Test	X ⁹						At the start of cycles 5 ⁹ , 9 ⁹ , 13 ⁹	X ⁹	X ¹⁰
Chest X-ray	X								
12-lead ECG	X ¹¹	X ¹¹	X ¹¹	X ¹¹	X ¹¹		At the start of each cycle ¹¹	X ¹¹	
LVEF and valves assessment (ECHO)	X ¹²						At the start of cycles 4 ¹² , 9 ¹²	X ¹²	

Time and Events Table for Full Study (Cycle = 28 days)									
Study Assessments ¹	Screen ²	Day 1 C1	Day 8 C1	Day 15 C1	Day 1 C2	Day 15 C2	D1 of C3-C16	End of Study Treatment	3-Month Off-study Follow-up
Serum (soluble BCMA)		X ¹³	X ¹³	X ¹³	X ¹³			X ¹³	
Serum (cytokines/chemokines)		X ¹⁴	X ¹⁴	X ¹⁴	X ¹⁴		Predose and EOI on D1 of each cycle	X	
Serum (anti-drug-antibodies)		X ¹⁵		X ¹⁵	X ¹⁵		At the start of cycles 3 ¹⁵ , 6 ¹⁵ , 9 ¹⁵ , 12 ¹⁵ and 16 ¹⁵	X	
Plasma-cfDNA		X						X	
Peripheral blood (flow for TBNK)		X ¹⁶	X ¹⁶		X ¹⁶		At the start of each cycle ¹⁶	X ¹⁶	
Sparse PK (blood)		X ¹⁷	X ¹⁷	X ¹⁷	X ¹⁷	X ¹⁷	C3D1 ¹⁷ , C3D15 ¹⁷ and C5D1 ¹⁷ only	X ¹⁸	
Genetics sample		X ¹⁹							
CT/PET Scan for disease assessments	X ²⁰						At the start of Cycles 3, 5, 7, 9, 11, 13, and 16		
Premedication if needed		X	X	X	X ²⁴	X	Each dosing week		
GSK2857916 administration		X ²¹	X ²¹	X ²¹	X ^{21, 24}	X	Each dosing week ²¹		
Steroid eye drops		X ²²	X ²²	X ²²	X ^{22, 24}	X ²²	Each dosing week ²²		
Tumor biopsy for BCMA expression	X ²³								
Adverse Events		Continuous							
Concomitant Medications	X	Continuous							
Survival Status									X ²⁵
Subsequent Treatment									X ²⁵

- Assessments scheduled on days of dosing should be done prior to drug administration, unless otherwise specified. All other assessments can be done \pm 3 days unless otherwise specified.
- All Screening assessments must be performed within 14 days prior to first dose unless otherwise specified. Informed Consent must be signed before any study-specific assessments are performed.
- Screening examination to include BCVA (best-corrected visual acuity), slit lamp examination (with special focus on cornea), intraocular pressure, and dilated fundoscopic examination may be performed within 21 days prior to first dose.
- On-study exams, to include BCVA (best-corrected visual acuity) and slit lamp examination (with special focus on cornea); window for exams is up to 3 days prior to dosing. In the event that a subject has a dose delay due to a non-ocular toxicity and an ocular exam has been performed for that cycle, a repeat ocular exam 3 days prior to dosing may be omitted if the participant did not have corneal signs on the previous exam and does not have any new corneal symptoms.

5. On initial (first infusion) dosing day, vital signs must be assessed at pre-dose (within 30 minutes prior to SOI), +10 minutes and +30 minutes after SOI (± 5 min), EOI, and 1 hour post EOI. On subsequent dosing days, vital signs must be assessed at pre-dose (within 30 minutes prior to SOI), +30 minutes after SOI, and EOI. **On days where vital sign timepoints align with PK sampling timepoints, vital signs should be assessed prior to PK samples being drawn.**
6. If completed within 72 hrs prior to the first dose, this assessment need not be repeated on Day 1 of Cycle 1. Refer to [Table 15](#) for comprehensive list of lab tests.
7. Troponin will be measured at the local (troponin I or T) and central (troponin I) lab. CK-MB at the local lab, or if not available by a central laboratory.
8. BNP to be measured locally, or if not available by a central laboratory, at screening; if cardiac workup is required due to safety concerns during the study, BNP should be measured.
9. Perform only in women of child-bearing potential. A serum pregnancy test should be performed at screening, and subsequent pregnancy tests may be either serum or urine
10. Final pregnancy test (serum or urine) must be performed in women of childbearing potential 60 days after last study treatment.
11. On dosing days, perform triplicate ECGs at predose (within 30 minutes prior to SOI) and EOI. **On days where ECG timepoints align with PK sampling timepoints, ECGs should be performed prior to PK samples being drawn (PK sample should be taken at the exact nominal time; refer to footnote 17).** At screening and End of Study, obtain a single ECG measurement.
12. At Screening, LVEF may be performed within 30 days prior to first dose. All ECHOs indicated on dosing days may be performed up to 7 days before dosing. ECHOs to be done locally and sent to GSK for central imaging storage.
13. A single sample for sBCMA will be collected at C1D8 predose, and at the End of Study visit. sBCMA samples will also be collected on C1D1 at predose (within 30 minutes prior to SOI) and EOI (± 5 minutes). On C1D15 and C2D1 collect at predose (within 30 minutes prior to SOI) and EOI (± 5 minutes)
14. Collect cytokines at predose (within 30 minutes prior to SOI) and EOI (± 5 min) (even when infusion is interrupted or halted) to assess allergic reaction.
15. All ADA samples will be collected prior to each infusion.
16. Sample(s) collected for analysis by central lab.
17. PK samples to be taken for both GSK2857916 and cys-mcMMAF measurement at C1D1 predose (within 30 minutes prior to SOI), EOI (just before EOI), 1 hour post EOI (± 5 min), and 3 hours post EOI (± 5 min); predose (within 30 minutes prior to SOI) and EOI (just before EOI) on C1D8, C1D15, C2D1, C2D15, C3D1, C3D15, and C5D1.
18. Collect 1 PK sample at each subject's final visit.
19. Informed consent for optional genetics research should be obtained before collecting a sample.
20. CT/PET scans from within 21 days prior to first dose are acceptable.
21. Study drug administration ± 1 day window only.
22. Prophylaxis with prednisolone phosphate 1% or dexamethasone 0.1% 1 drops QID x 4 days starting 1 day prior to treatment.
23. Archived or fresh tissue required for BCMA testing. Refer to Section [5.2.1](#) Inclusion Criterion #4 for eligibility criteria.
24. Also applies to C2D8.
25. Record subject's survival status and whether subsequent treatment for disease was given. Subject does not need to come in for visit.

Abbreviations:

ADA = Antibody Drug Antibody; ALP = alkaline phosphatase; BCVA = best corrected visual acuity; BNP = B-type natriuretic peptide; C1D1 = Cycle 1 Day 1, etc.; cfDNA = Circulating free DNA; CK = creatine kinase; CRP = C-reactive protein; EOI = End of Infusion; PD = Pharmacodynamics; PK = Pharmacokinetics; QID = 4 times a day; SOI = start of infusion

7.2. Demographic/Medical History and Baseline Assessments

The following demographic parameters will be captured during Screening: date of birth, gender, race and ethnicity.

Medical/medication history assessed as related to the eligibility criteria listed in Section [5.2](#).

Baseline (Screening) assessments obtained will include:

- Complete physical examination, including height (in cm) and weight (in kg).
- Vital signs (blood pressure, temperature, pulse rate)
- Chest x-ray
- Ocular exam
- Eastern Cooperative Oncology Group (ECOG) performance status
- Clinical laboratory tests outlined in [Table 15](#)
- Serum beta-human chorionic gonadotropin (β -HCG) pregnancy test for female subjects of childbearing potential only
- 12-lead electrocardiogram (ECG)
- Echocardiogram (ECHO)
- Imaging studies (extramedullary disease for MM if indicated, or CT/PET scan for lymphomas)
- For MM: BM aspirate for FISH, BCMA (flow cytometry), PD (target engagement and caspase 3); BCMA expression (IHC)
- For MM: BM biopsy for disease assessment
- For Lymphomas: archival or fresh tissue evaluation for BCMA expression
- Review of concomitant medications

Procedures conducted as part of the subject's routine clinical management (e.g., blood count, imaging study) and obtained prior to signing of informed consent may be utilized for Screening or baseline purposes provided the procedure meets the protocol-defined criteria and has been performed in the timeframe of the study.

7.2.1. Critical Baseline Assessments

Cardiovascular medical history/risk factors will be assessed at baseline.

7.3. Safety Evaluations

Planned time points for all safety assessments are provided in the Time and Events Tables (Section [7.1](#)).

7.3.1. Physical Examinations

At screening and on dosing days, a full physical examination will include assessments of the head, eyes, ears, nose, throat, skin, thyroid, lungs, cardiovascular, abdomen (liver and spleen), lymph nodes and extremities. Height and weight will also be measured and recorded.

During interim visits and at the end of study, a brief physical examination will include assessments of the skin, lungs, cardiovascular system, and abdomen (liver and spleen).

7.3.2. ECOG Performance Status

The performance status will be assessed using the Eastern Cooperative Oncology Group (ECOG) scale ([Appendix 6](#)) as specified in the Time and Events Tables (Section [7.1](#)).

7.3.3. Vital Signs

Vital sign measurements will include systolic and diastolic blood pressure, temperature, and pulse rate. Vital signs should be measured after resting for at least 5 minutes. Vital signs will be measured more frequently if warranted by the clinical condition of the subject. On days where vital signs are measured multiple times, temperature does not need to be repeated unless clinically indicated.

First Infusion:

Monitoring intervals: Vital signs must be monitored at predose (within 30 minutes prior to start of infusion), +10 and +30 minutes post start of infusion, and at the end of infusion, and 1 hour post end of infusion. In general, subjects must also be monitored for at least 1 hour after the completion of the first infusion and may be discharged if considered clinically stable and all other study procedures have been completed.

Sentinel subject: Subject must be monitored for at least 24 hours post first infusion.

Subsequent subjects: Subjects may be discharged if considered clinically stable and all other study procedures have been completed.

Subsequent Infusions:

Monitoring intervals: Vital signs must be monitored at predose (within 30 minutes prior to start of infusion), +30 minutes post start of infusion, and at the end of infusion.

Subjects may be discharged after the infusion has been completed if considered clinically stable and all other study procedures have been completed.

In case of infusion related reactions or cytokine storm, monitoring will be performed with higher frequency (as clinically indicated).

7.3.4. Electrocardiogram

Triple 12-lead electrocardiogram (ECGs) will be obtained at designated time points specified in the Time and Events Tables (Section [7.1](#)) during the study using an ECG

machine that automatically calculates the heart rate and measures PR, QRS, QT, and corrected QT (QTc) intervals. At each assessment a 12-lead ECG will be performed by qualified personnel at the site after the subject has at least a 5 minute rest.

The QT interval should be corrected for heart rate by Fridericia's formula (QTcF). Refer to Section 3.9.2 for QTc withdrawal criteria. Refer to the Study Procedures Manual (SPM) for details regarding ECG procedures.

7.3.5. Echocardiogram

Echocardiograms (ECHOs) will be performed at baseline to assess cardiac ejection fraction and cardiac valve morphology for the purpose of study eligibility, as specified in the Time and Events Tables (Section 7.1). Additional ECHO assessments will be performed at specified timepoints indicated in the Time and Events Tables (Section 7.1) or if clinically warranted. The evaluation of the echocardiographer should include an evaluation for left ventricular ejection fraction (LVEF) and both right and left-sided valvular lesions.

Copies of all ECHOs performed on subjects will be stored in a central location if further evaluation is warranted.

7.3.6. Ocular Exam

An ocular exam to include BCVA (best-corrected visual acuity), slit lamp examination (with special focus on the cornea), intraocular pressure, and dilated funduscopy examination will be conducted for all subjects at screening. Additional exams will be performed as specified in the Time and Events Tables (Section 7.1) during the treatment period and at monthly follow-up visits as clinically indicated.

7.3.7. Laboratory Assessments

All protocol required laboratory assessments, as defined in (Table 15), should be performed according to the Time and Events Tables (Section 7.1). Details for the preparation and shipment of samples will be provided in the SPM.

Prior to administration of the first dose of study treatment, results of laboratory assessments should be reviewed. Any laboratory test with a value outside the normal range may be repeated (prior to the first dose) at the discretion of the investigator.

If additional non-protocol specified laboratory assessments are performed at the institution's local laboratory and result in a change in patient management or are considered clinically significant by the Investigator (for example SAE or AE or dose modification) the results must be recorded in the subject's CRF. Refer to the SPM for appropriate processing and handling of samples to avoid duplicate and/or additional blood draws.

All laboratory tests with values that are significantly abnormal during participation in the study or within 30 days after the last dose of study treatment should be repeated until the values return to normal or baseline. If such values do not return to normal within a period judged reasonable by the investigator, the etiology should be identified and the sponsor notified.

Hematology, clinical chemistry, urinalysis and additional parameters to be tested are listed in [Table 15](#):

Table 15 List of Clinical Laboratory Tests

Hematology			
Platelet Count		RBC Indices:	Automated WBC Differential:
Red blood cell (RBC) Count		MCV	Neutrophils
White blood cell (WBC) Count (absolute)		MCH	Lymphocytes
Reticulocyte Count		MCHC	Monocytes
Hemoglobin			Eosinophils
Hematocrit			Basophils
Clinical Chemistry			
Blood urea nitrogen (BUN)	Potassium	Aspartate aminotransferase (AST)	Total and direct bilirubin
Creatinine	Chloride	Alanine aminotransferase (ALT)	Uric Acid
Glucose	Total carbon dioxide (CO ₂)	Gamma glutamyl transferase (GGT)	Albumin
Sodium	Calcium	Alkaline phosphatase	Total Protein
Magnesium	Phosphorous	Creatine kinase (CK)	LDH
Routine Urinalysis			
Specific gravity			
pH, glucose, protein, blood and ketones by dipstick			
Microscopic examination (if blood or protein is abnormal)			
24-hour urine protein and albumin			
Other screening tests			
Hepatitis B (HBsAg)			
Hepatitis C (Hep C antibody -- if second generation Hepatitis C antibody positive, a hepatitis C antibody Chiron RIBA immunoblot assay or a validated HCV PCR viral test should be reflexively performed on the same sample to confirm the result)			
Follicle stimulating hormone (FSH) and estradiol (as needed in women of non-child bearing potential only)			
FISH analysis ¹			
Other Laboratory Tests			
Troponin	PTT	INR	IgG, IgM, IgA
CK-MB	B-type natriuretic peptide	C-reactive protein (CRP)	Beta2 microglobulin
Kappa, lambda free LC, FLC ratio	ADA	PGx ²	Immunofixation
Serum Protein Electrophoresis (SPEP) and Serum M-protein calculation	Urine Protein Electrophoresis (UPEP)		
Biomarker Measurements			
BCMA/sBCMA	Caspase 3	Serum cytokines/chemokines	cfDNA

1. FISH testing at least for: t(4;14), t(14/16), 17p13del. Biopsy samples from within 60 days prior to first dose are acceptable.

2. Samples to be collected from subjects in expansion cohorts only.

7.3.8. Pregnancy Testing and Reporting

The need for a screening pregnancy test depends on whether a female subject is of childbearing potential or non-childbearing potential.

If a female subject is of childbearing potential, she must have a serum β -HCG pregnancy test performed within 14 days prior to the first dose of study treatment. Subjects with positive pregnancy test result must be excluded from the study. Subjects with negative pregnancy test result must agree to use an effective contraception method as described below during the study until 60 days following the last dose of study treatment(s).

Any pregnancy that occurs during study participation must be reported using a clinical trial pregnancy form. To ensure subject safety, each pregnancy must be reported to GSK within 2 weeks of learning of its occurrence. The pregnancy must be followed up to determine outcome (including premature termination) and status of mother and child. Pregnancy complications and elective terminations for medical reasons must be reported as an adverse event (AE) or serious adverse event (SAE). Spontaneous abortions must be reported as an SAE.

Any SAE occurring in association with a pregnancy brought to the investigator's attention after the subject has completed the study and considered by the investigator as possibly related to the study treatment, must be promptly reported to GSK.

In addition, the investigator must attempt to collect pregnancy information on any female partners of male study subjects who become pregnant while the subject is enrolled in the study. Pregnancy information must be reported to GSK as described above.

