1.2.6. Genotoxicity

Intact biopharmaceutical therapeutics, such as monoclonal antibodies and antibody drug conjugates, do not directly interact with DNA or other chromosomal material. Therefore, genetic toxicology studies with GSK2857916 were not performed. The active moiety of GSK2857916 is MMAF cytotoxin which is expected to be genotoxic in mammalian systems given it is a microtubule disrupting agent.

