target engagement/tumor cell killing) will be estimated/measured during dose escalation to inform the next cohort dose and the selection of a RP2 dose [Biologically effective dose (BED) or maximum tolerated dose (MTD)]. In case of insufficient sample quality or due to high variability in the measurement of PD biomarkers, up to 6 additional samples from subjects in expansion cohort might be collected for PD analysis. Initially, GSK2857916 will be administered (IV) via 60 min infusion once every three weeks (21 days = 1 cycle) on Schedule 1. Once an MTD1 or RP2D has been established on the once every 21-day (Schedule 1), the safety, tolerability, PK, and PD of once-weekly dosing (Schedule 2) of GSK2857916 may be explored as an additional cohort(s). Dose escalation decisions on each of these two dosing schedules will utilize a separate N-CRM model. The information gained from evaluation of Schedule 1 (once every three weeks; 21-day cycle) will be utilized to inform the model for Schedule 2 (once weekly for three consecutive weeks, 1 week rest; 28-day cycle).

[figure not shown]
Part 2: Expansion cohorts will assess the safety, tolerability, PK (sparse sampling), and clinical activity of the GSK2857916 dose regimen identified in Part 1. A total of approximately 50 subjects will be enrolled in Part 2. A MM cohort (up to 40 subjects) will be enrolled with no prospective BCMA screening required (BCMA expression data collection and retrospective analysis will be performed). In addition, futility analyses will be performed on the MM cohort after approximately 15, 22 and 30 evaluable patients have been assessed for response. For more detailed information on the futility analysis, see Section 13.6.2. Sparse PK sampling will be collected to further characterize GSK2857916 exposure for the selected dose schedule.

A smaller cohort of subjects with BCMA positive lymphomas (up to 10 subjects) will be enrolled based upon prospective detection of positive BCMA tumor cell expression as determined by a central laboratory using a validated IHC assay.

Protocol waivers or exemptions are not allowed. Therefore, adherence to the study design requirements, including those specified in the Time and Events Tables (Section 7.1) are essential.

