5.2. Subject Selection Criteria

5.2.1. Inclusion Criteria

Specific information regarding warnings, precautions, contraindications, adverse events (AEs), and other pertinent information on the GSK study treatment that may impact subject eligibility is provided in the Investigator Brochure (IB)/IB supplement(s). Deviations from inclusion criteria are not allowed because they can potentially jeopardize the scientific integrity of the study, regulatory acceptability or subject safety. Therefore, adherence to the criteria as specified in the protocol is essential.

Subjects eligible for enrolment in the study must meet all of the following criteria:

1. Provide signed written informed consent, which includes compliance with the requirements and restrictions listed in the consent form
2. Male or female, 18 years or older (at the time consent is obtained)
3. Eastern Cooperative Oncology Group (ECOG) performance status of 0 or 1 ([Appendix 6](#))
4. **Part 1/dose escalation:**
 - Histologically or cytologically confirmed diagnosis of: Multiple Myeloma in a subject who fulfills **all** of the following:
 - has undergone stem cell transplant, or is considered transplant ineligible,
 - has been pretreated with at least the 3 following classes of anti-myeloma drugs: alkylators, proteasome inhibitors and immunomodulators,

- has demonstrated progression on, or within 60 days of completion of the last therapy.

Part 2 /MM cohort:

- Histologically or cytologically confirmed diagnosis of: Multiple Myeloma in a subject who fulfills **all** of the following:
- has undergone stem cell transplant, or is considered transplant ineligible,
- has been pretreated with at least the 3 following classes of anti-myeloma drugs: alkylators, proteasome inhibitors and immunomodulators,
- and has demonstrated progression on, or within 60 days of completion of the last therapy.
- AND has measurable disease with at least one of the following:
 - a. Serum M-protein ≥ 0.5 g/dL (≥ 5 g/L)
 - b. Urine M-protein ≥ 200 mg/24h
 - c. Serum FLC assay: Involved FLC level ≥ 5 mg/dL (≥ 50 mg/L) and an abnormal serum free light chain ratio (< 0.26 or > 1.65)
 - d. Biopsy proven plasmacytoma (should be measured within 28 days of Screening Visit)

or

Part 2/ BCMA positive Lymphoma cohort:

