- Non-childbearing potential (i.e. physiologically incapable of becoming pregnant) defined as pre-menopausal females with a documented tubal ligation or hysterectomy; or postmenopausal defined as 12 months of spontaneous amenorrhea [in questionable cases a blood sample with simultaneous follicle stimulating hormone (FSH) > 40 MIU/mL and estradiol < 40 pg/mL (<147 pmol/L) is confirmatory]. Females on hormone replacement therapy (HRT) and whose menopausal status is in doubt will be required to use one of the contraception methods specified if they wish to continue their HRT during the study. Otherwise, they must discontinue HRT to allow confirmation of post-menopausal status prior to study enrollment. For most forms of HRT, at least 2-4 weeks will elapse between the cessation of therapy and the blood draw; this interval depends on the type and dosage of HRT. Following confirmation of their

- post-menopausal status, they can resume use of HRT during the study without use of a contraceptive method.
- Women of childbearing potential must have a negative serum pregnancy test within 72 hours of first dose of study treatment and agree to use effective contraception, as defined in Section 11.1.1, during the study and for 60 days following the last dose of study treatment.
8. Men with a female partner of childbearing potential must have either had a prior vasectomy or agree to use effective contraception as described in Section 11.1.2 from the time of first dose of study until 60 days after the last dose of study treatment to allow for clearance of any altered sperm.
 9. All prior treatment-related toxicities (defined by National Cancer Institute-Common Toxicity Criteria for Adverse Events (NCI-CTCAE), version 4) must be \leq Grade 1 at the time of enrollment except for alopecia, and grade 2 neuropathy

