Serum (cytokines/chemokines)		X ¹⁹	X			X ¹⁹	At predose and EOI on D1 of each cycle	X	
Serum (anti-drug-antibodies)	X					X ²⁰	At the start of cycles 3 ²⁰ , 6 ²⁰ , 9 ²⁰ , 12 ²⁰ and 16 ²⁰	X	
Plasma-cfDNA	X							X	
Peripheral blood (flow for TBNK)	X ¹⁵					X ¹⁵	At the start of each cycle ¹⁵	X ¹⁵	
Serial Pharmacokinetics (blood)		X ²¹	X ²¹	X ²¹	X ²¹	X ²¹	C3D1 only ²¹	X ²²	
Urine PK	X ²³					X ²³	Day 1 of cycles 4 ²³ , 7 ²³ , 10 ²³ , 13 ²³ , 16 ²³		
Premedication if needed		X				X	At the start of each cycle		
GSK2857916 administration		X ²⁴				X ²⁴	X ²⁴		
Steroid eye drops		X ²⁵				X ²⁵	X ²⁵		
Adverse Events							Continuous		

Time and Events Table for Full Study (Cycle = 21 days)										
Study Assessments ¹	Screen ²	Day 1 C1	Day 2 C1	Day 8 C1	Day 15 C1	Day 1 C2	D1 of C3-C16	End of Study Treatment	3-Month Off-study Follow-up	
Concomitant Medications	X	Continuous								
Survival Status									X ²⁶	
Subsequent Treatment									X ²⁶	

- Assessments scheduled on days of dosing should be done prior to drug administration, unless otherwise specified. All other assessments can be ± 3 days of scheduled occurrence unless otherwise specified.
- All Screening assessments must be performed within 14 days prior to first dose unless otherwise specified. Informed Consent must be signed before any study-specific assessments are performed.
- Screening examination to include BCVA (best-corrected visual acuity), slit lamp examination (with special focus on cornea), intraocular pressure, and dilated fundoscopic examination may be performed within 21 days prior to first dose.
- On-study exams to include BCVA (best-corrected visual acuity) and slit lamp examination (with special focus on cornea); window for exams is up to 3 days prior to dosing.
- On initial (first infusion) dosing day, vital signs must be assessed at pre-dose (within 30 minutes prior to SOI), +10 minutes and +30 minutes (± 5 min) after SOI, EOI, and 1 hour post EOI. On subsequent dosing days, vital signs must be assessed at pre-dose (within 30 minutes prior to SOI), +30 minutes after SOI, and EOI. The Sentinel Subject must be observed for at least 24 hours post EOI. **On days where vital sign timepoints align with PK sampling timepoints, vital signs should be assessed prior to PK samples being drawn.**
- If completed within 72 hrs prior to the first dose, this assessment need not be repeated on Day 1 of Cycle 1. Refer to [Table 15](#) for comprehensive list of lab tests.

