- Troponin will be measured at the local lab (troponin I or T) and a central lab (troponin I). CK-MB at the local lab or if not possible by a central laboratory.
- BNP to be measured locally, or if not available by a central laboratory, at screening; if cardiac workup is required due to safety concerns during the study, BNP should be measured.
- Perform only in women of child-bearing potential. A serum pregnancy test should be performed at screening, and subsequent pregnancy tests may be either serum or urine;
- Final pregnancy test (serum or urine) must be performed in women of childbearing potential 60 days after last study treatment.
- On dosing days, ECG to be performed in triplicate at predose (within 30 minutes prior to SOI) and EOI. **On days where ECG timepoints align with PK sampling timepoints, ECGs should be performed prior to PK samples being drawn (PK sample should be taken at the exact nominal time; refer to footnote 21).** At screening, on interim visits (C1D8 and C1D15) and End of Study obtain a single ECG measurement.
- At Screening, LVEF may be performed within 30 days prior to first dose. All ECHOs indicated on dosing days may be performed up to 5 days before dosing. All ECHOs to be done locally and sent to GSK for central imaging storage.
- May be performed up to 21 days prior to C1D1 as screening value. Needs to be performed by the same method throughout the study as was done at baseline (i.e. if PET scan was used as baseline, subject needs to be followed by PET scans). Selected target lesion needs to be measured and followed over time.
- Samples from within 14 days prior to first dose are acceptable.
- Sample(s) collected for analysis by central lab. The same sample will be used for BCMA (flow) and PD during Screening. On D8 only postdose PD assessment will be performed
- FISH testing at least for: t(4;14), t(14;16), 17p13del. FISH results from samples taken within 60 days prior to first dose are acceptable.

17. Archival tissue from up to 60 days prior to study is acceptable
18. A single sample for sBCMA will be collected at C1D8, C1D15 and at the End of Study visit. sBCMA samples will also be collected on C1D1 at predose (within 30 minutes prior to SOI), at EOI (± 5 minutes) and on C1D2 24h post SOI. On C2D1 sBCMA will be collected pre-dose (within 30 minutes prior to SOI) and at the EOI (± 5 minutes)

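### Section 7.3.8 allows the pre-dose serum pregnancy test to be 14 days old, while inclusion criterion 7 requires a negative serum test within 72 hours of first dose

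*Protocol*

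**What the plan says.** Section 7.3.8, the section devoted to pregnancy testing, requires of women of childbearing potential a serum "pregnancy test performed within 14 days prior to the first dose of study treatment". It attaches no qualifier and does not refer to the eligibility criteria for a shorter limit.

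Inclusion criterion 7, worded identically in the synopsis and in Section 5.2.1, reads: "Women of childbearing potential must have a negative serum pregnancy test within 72 hours of first dose of study treatment". Section 5.2.1 also says "Deviations from inclusion criteria are not allowed", and Section 3.1 adds "Protocol waivers or exemptions are not allowed".

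Section 7.2 lists the serum "pregnancy test for female subjects of childbearing potential only" among the baseline (screening) assessments. Footnote 2 of the Time and Events Tables gives the general rule: "All Screening assessments must be performed within 14 days prior to first dose unless otherwise specified". The pregnancy-test footnote gives no window of its own: "A serum pregnancy test should be performed at screening, and subsequent pregnancy tests may be either serum or urine".

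**The concern.** Two current rules set different maximum ages for the same test. A site that takes its instructions from the dedicated testing section and the visit schedule could give the first dose on a result that does not satisfy a criterion from which no departure is permitted.

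The point bears on safety as well as consistency. This is a first-in-human study of a conjugate carrying an "MMAF cytotoxin which is expected to be genotoxic in mammalian systems" (Section 1.2.6). The older the test, the longer the interval in which an early pregnancy could go undetected before exposure.

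**Working it through.** There is no design figure to reproduce. The check sets the rules side by side and asks whether anything else in the protocol reconciles them.

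**Inputs**

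| Source | Test | Maximum age at first dose |
|---|---|---|
| Criterion 7 (synopsis and Section 5.2.1) | Serum, negative | 72 hours |
| Section 7.3.8 | Serum | 14 days |
| Time and Events Tables, footnote 2 | Any screening assessment | 14 days by default, yielding to a more specific rule |
| Time and Events Tables, pregnancy-test footnote | Serum at screening | None stated |

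**Size of the gap**

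- Section 7.3.8: 14 × 24 = 336 hours.
- Criterion 7: 72 hours.
- Difference: 336 − 72 = 264 hours, or 264 / 24 = 11 days.

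Tests aged 0 to 72 hours meet both rules. Tests aged more than 72 and up to 336 hours meet Section 7.3.8 and fail criterion 7.

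**Is Section 7.3.8 only the screening rule, with a second test to follow?** The schedule does not support that reading.

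- In all six tables (7.1.1.1, 7.1.1.2 and 7.1.2.1 to 7.1.2.4) the pregnancy row has one pre-dose entry, at Screening. The next entry is Cycle 5.
- All six blood-volume tables in Appendix 10 (Sections 16.9.1.1 to 16.9.1.6) allot 2 ml for the pregnancy test at Screening and nothing in Cycle 1.
- Where the schedule intends a 72-hour limit, it says so. Hematology, chemistry, urine dipstick and INR/PTT have a Cycle 1 Day 1 entry, with footnote 6 waiving the repeat if the test was done in the preceding 72 hours. The pregnancy test has neither the entry nor the footnote.

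**Do the tables themselves contradict criterion 7?** No. Footnote 2 is a default that gives way to a specific rule, and criterion 7 is one. The tables simply do not prompt for the 72-hour limit. The direct conflict lies in Section 7.3.8, which fixes 14 days for this particular test without any such proviso.

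**How many women?** The protocol gives no count. The maximum number of myeloma subjects is 30 + 15 + 40 = 85; with up to 10 lymphoma subjects the total is 95. Section 1.1 puts the median age at myeloma diagnosis at about 70 years, so the number of childbearing potential is likely small.

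**The case against.** The strongest reply is that the two rules can both be obeyed. Section 7.3.8 states a necessary condition and never says that meeting it is enough for eligibility or dosing. The inclusion criteria are the gate that cannot be waived, so it is clear which rule governs, and a site that meets criterion 7 cannot breach Section 7.3.8. That is correct, and it means no site is properly permitted to dose on a 14-day-old test. It does not remove the defect: the section a site would consult for pregnancy testing states the looser limit, does not mention the stricter one, and is supported by a schedule that does not prompt for it.

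Harm would also require several checks to fail. Criterion 7 appears twice. The Medical Monitor must approve the screening packet before a subject number is assigned (Section 12.1). Laboratory results should be reviewed before first dose (Section 7.3.7, which sets no limit on the age of a test). Pregnancy is an exclusion (criterion 13). Women relying on abstinence must abstain for 14 days beforehand (Section 11.1.1), although that covers only this group. These safeguards stand, and they are why the point is minor.

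A third point concerns the remedy. If the only scheduled test moves to within 72 hours of dosing, its result may not be ready when the packet is reviewed. That is a fair practical consideration, and the alternative under the fix meets it.

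**Conclusion.** The inconsistency is real and lies in current text. Section 7.3.8 gives a pregnancy-test window 264 hours (11 days) wider than criterion 7, and nothing in the schedule closes the gap. It is a minor safety and eligibility inconsistency. No endpoint, error rate or dose-escalation decision is affected.

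The conclusion rests on reading criterion 7 as meaning the 72 hours before first dose, and on the Time and Events Tables being the full schedule of pregnancy tests. The statement that few women are affected is an inference from the disease and its age at diagnosis, not a figure in the protocol.

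**What to change.** Keep criterion 7 as it stands.

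1. In Section 7.3.8, replace the 14-day window with 72 hours.
2. In the pregnancy-test footnote of each Time and Events Table, state that the pre-dose test must be a serum test done within 72 hours before first dose. This is footnote 9 in 7.1.1.1, 7.1.1.2, 7.1.2.2 and 7.1.2.4, and footnote 10 in 7.1.2.1 and 7.1.2.3.

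If the sponsor prefers to keep an early screening test so that the result is in the packet, add a repeat test (for example at Cycle 1 Day 1, before dosing) whenever the first would be more than 72 hours old. Section 7.3.8 should then describe both tests. The repeat must be specified as serum, because the existing footnotes allow either serum or urine for any test after screening.

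The cost is one phrase in Section 7.3.8, one phrase in each of six footnotes, and at most one repeat serum test (2 ml by Appendix 10) for a few women.
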